2.4.4.1.3 Subgroup analyses

Where appropriate for the size of a subgroup (at least 30 patients in each category), exploratory analyses will be performed on the primary endpoint to summarize the treatment effects across subgroups defined by the following baseline and screening factors:

- Duration of diabetes (<10/>=10 years),
- Gender,
- Randomization strata of screening HbA1c categories (< 8.0% versus $\ge 8.0\%$),
- BMI (<30 and \geq 30 kg/m²).

Categories for subgroup analyses may be adapted according to data.

For each subgroup, the primary efficacy endpoint using available data from the 12-week randomized period in ITT population will be analyzed via an analysis of covariance (ANCOVA) including the fixed categorical effects of treatment group (Toujeo, Tresiba), randomization stratum of screening HbA1c (<8.0% versus $\geq 8.0\%$), the continuous fixed covariate of baseline percent time in range value, and adding the corresponding subgroup factor and subgroup factor-by-treatment interaction. LSmeans treatment difference (with the corresponding SEs and 95% CI) will be presented for each subgroup. The P-value for the interaction fixed term will be

obtained in order to evaluate whether the corresponding subgroup is behaving as a response modifier.

The ESTIMATE statement in PROC GLM, which reflects the subgroup analyses by baseline and screening factors, will be used. An example of SAS code for the subgroup analysis by gender is provided below:

Female group:

```
ESTIMATE "TOUJEO-TRESIBA" ARM 1 -1 SEX*ARM 1 0 -1 0;
```

Male group:

```
ESTIMATE "TOUJEO-TRESIBA" ARM 1 -1 SEX*ARM 0 1 0 -1;
```

Forest plot will be provided.

Further subgroup analyses may be performed if deemed necessary for the interpretation of results.

2.4.4.2 Analyses of secondary efficacy endpoints

Secondary efficacy endpoints analysis will be done on the ITT population, with no multiple imputation except for the main secondary endpoint 'Glucose total CV', for which a similar procedure as for the primary endpoint applies as it is part of the multiplicity procedure. No sensitivity analyses are planned for secondary endpoints.

2.4.4.2.1 CGM secondary endpoints

The CGM endpoints will be analyzed using an ANCOVA model

- Glucose total CV (main secondary endpoint)
- Glucose within-day and between-day CV
- Percent time and mean hours per day with glucose <70 mg/dL (on all time and during the night [00:00 to 05:59])
- Percent time and mean hours per day with glucose >180 mg/dL

The ANCOVA model to perform the analysis includes the fixed categorical effects of treatment group (Toujeo, Tresiba), randomization stratum of screening HbA1c (< 8.0% versus $\geq 8.0\%$), as well as the continuous fixed covariate of baseline value for the corresponding endpoints.

For glucose total CV (main secondary endpoint), and if the non-inferiority on the primary endpoint is demonstrated, the non-inferiority will be tested. But, unlike TIR, for CV the lower the better. Therefore, the non-inf comparison will be based on:

H0: m1 - 1.1 × m0 \ge 0

For the other secondary endpoints, LSmeans treatment difference (with the corresponding SEs and 95% CI) will be provided and the p-value (of the difference between the two treatments) will be provided for descriptive purpose only (see Section 2.4.4.4).

2.4.4.2.2 HbA1c

Change in HbA1c will be analyzed using an ANCOVA model including the fixed categorical effects of treatment group (Toujeo, Tresiba) as well as the continuous fixed covariate of baseline HbA1c value; LSmeans treatment difference (with the corresponding SEs and 95% CI) will be provided and p-value (of the difference between the two treatments) will be provided for descriptive purpose.

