6.3 MEASURES TO MINIMIZE BIAS: RANDOMIZATION AND BLINDING

As Toujeo and the control drug Tresiba are distinguishable, this study is an open-label design, and no attempt will be made to blind the randomly assigned study treatment.

The Clinical Supplies Trial Supply Operations Manager will provide the treatment kit number list and the Study Biostatistician will provide the randomization scheme to the IRT. IRT will then generate the patient randomization list according to which it will allocate patients to either treatment arm.

The IMPs will be provided in open-label boxes and each type of kit is identified with a treatment number.

At the screening visit, the Investigator or designee will contact the IRT center to receive the patient number. This patient number is composed of a 12-digit number containing the 3-digit country code, 4-digit center code, and the 5-digit patient chronological number (which is 00001 for the first patient screened in a center, 00002 for the second patient screened in the same center, etc).

Patients can be re-screened once before randomization in case of non-eligibility or in cases where original screen failure was due to reasons expected to change at rescreening and based upon the Investigator's clinical judgment. Re-screened patients will be subject to the screening visit procedures/assessments including new informed consent signed and allocation of a new patient number.

Before randomization, baseline CGM results with accompanying CGM summary report certifying compliance with requirements MUST be available. In order for a patient to be randomized the baseline CGM performance (during Weeks -3 to -1) must reflect at least 10 days (not necessarily consecutive) of useable 24-hour CGM data (see Section 8.1.1.2 for the definition of useable data).

At Visit 6, only after patient eligibility is confirmed, the Investigator or designee will call the IRT for patient randomization and first treatment kit(s) allocation.

Only eligible patients will be randomized at a 1:1 ratio to receive Toujeo or Tresiba for 12 weeks. Randomization will be stratified by HbA1c at screening (<8.0%; $\ge8.0\%$).

A randomized patient is defined as a patient who is registered and assigned with a randomized treatment arm from the IRT, as documented from IRT log file, regardless of whether the treatment kit was used or not.

The IRT will be contacted at each time a treatment kit(s) allocation is necessary, ie, at Visit 6 (randomization) and also at Visit 14.

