8.1.2 Glycated hemoglobin A1c

Glycated hemoglobin A1c is assayed at screening (Visit 1; Week -6/-5), randomization Visit 6 and Visit 18 (Week 12). For the eligibility and efficacy assessments of the study, HbA1c is measured by a certified level I "National Glycohemoglobin Standardization Program", or equivalent certification as per specific country regulations, central laboratory. The screening value will be transferred into the IRT for stratification purpose during the patient randomization at the Visit 6.

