9.4.1 Efficacy analyses

All efficacy analyses will be performed on the ITT population. Sensitivity analyses will be performed on the PP population on a selection of endpoints.

31-May-2019 Version number: 1

Table 7 - Efficacy analyses

Endpoint	Statistical Analysis Methods		
Primary: Percent time in glucose range of ≥70 to ≤180 mg/dL (≥3.9 to ≤10 mmol/L) at Week 12, obtained using CGM	Primary endpoint using available data from the 12-week randomized period will be analyzed using an ANCOVA model including the fixed categorical effects of treatment group (Toujeo, Tresiba), randomization stratum of screening HbA1c (<8.0% versus ≥8.0%), as well as, the continuous fixed covariate of baseline percent time in range value. This procedure will provide baseline adjusted least-squares means estimates at Week 12 for both treatment groups, as well as, the differences of these estimates, with their corresponding standard errors (SEs) and 95% CIs.		
	To assess non-inferiority, the lower bound of the two-sided 95% CI for the adjusted difference estimate of m1 - 0.9*m0 at Week 12 will be compared to 0.		
	Non-inferiority will be demonstrated if the lower bound of the two-sided 95% CI of the adjusted difference estimate of m1 - 0.9*m0 at Week 12 on the ITT population is >0.		
	A sensitivity analysis will be performed using the PP population.		
	Let m1 and m0 be the true means for the Toujeo and Tresiba groups, respectively.		
	To assess non-inferiority, the lower bound of the two-sided 95% CI for the adjusted difference estimate of m1 - 0.9*m0 at Week 12 will be compared to 0.		
	Non-inferiority will be demonstrated if the lower bound of the two-sided 95% CI of the adjusted difference estimate of m1 - 0.9*m0 at Week 12 on the ITT population is >0.		
	A sensitivity analysis will be performed using the PP population.		
Secondary: CGM endpoints at Week 12 (see Section 3)	CGM endpoints will be analyzed using the same model as described for the primary endpoint using the ITT population.		
` , , , , , , , , , , , , , , , , , , ,	Exploratory analysis will be performed on within day glucose CV to summarize the treatment effects across subgroup defined by within day CV<36% vs. >=36% at baseline.		
Secondary			
 Change from baseline to Week 12 in HbA1c 	Change in HbA1c will be analyzed using an analysis of covariance (ANCOVA) model including fixed categorigal effect of treatment group (Toujeo, Tresiba), as well as, the continuous fixed covariate of baseline HbA1c value.		

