2 STATISTICAL AND ANALYTICAL PROCEDURES

2.1 ANALYSIS ENDPOINTS

2.1.1 Demographic and baseline characteristics

The baseline value is the last available value obtained up to the date and time of randomization or up to the time of first injection of the treatment if the measurement occurred on the same day as randomization.

All baseline safety and efficacy parameters (apart from those listed below) are presented along with the summary statistics in the safety and efficacy sections (Section 2.4.5 and Section 2.4.4).

Demographic characteristics

Demographic variables are:

- Gender (Male, Female),
- Age in years at date of informed consent (quantitative and qualitative variable: from 18 64 and 65 years and over),
- Weight in kg (quantitative),
- BMI in kg/m² (quantitative and qualitative variable: <25, ≥25 < 30, ≥30 <35, and ≥35 kg/m²),
- Randomization strata of screening HbA1c categories (<8.0 and $\geq 8.0\%$).

Medical or surgical history

Medical (or surgical) history includes any past and/or concomitant diseases or past surgeries.

This information will be coded using the version of Medical Dictionary for Regulatory Activities (MedDRA) currently in effect at Sanofi at the time of database lock.

Disease characteristics at baseline

Specific disease history includes:

- Time from diagnosis to randomization (years) and age at diagnosis (years),
- History of gestational diabetes (yes, no),
- Time from first intake of basal insulin analog and of rapid acting insulin analog to randomization (years),
- Screening basal insulin analog (treatment preferred name according to the World Health Organization-Drug Dictionary [WHO-DD]). Distinction between insulin glargine U100 and insulin glargine U300 will be provided,

- Screening basal insulin dose, as reported on screening visit and in case of several lines reported the last available will be used (total daily dose in IU, total daily dose adjusted for body weight, in IU/kg),
- Screening mealtime insulin analog (Insulin glulisine, Insulin lispro, Insulin aspart),
- Screening mealtime insulin dose, as reported on screening visit and in case of several lines reported the last available will be used (total daily dose in IU, total daily dose adjusted for body weight, in IU/kg),
- Screening total daily insulin dose, ie, the day of screening visit (basal + mealtime) in IU and adjusted for body weight in IU/kg,

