2.3.1.2 Per-protocol population

The per-protocol population (PP) is a subset of the ITT population which will comprise all randomized patients, who are exposed, who do not permanently discontinued IMP allocated by IRT, who completed the study as per protocol (as reported in the EOS page) and who do not present any major protocol deviations that potentially impact the primary efficacy results, as presented below:

• Major or critical deviation linked to inclusion criteria:

- From inclusion criterion I02: Patients without T1DM.
- From inclusion criterion I03: Not treated with multiple daily injections (MDI) using basal insulin analog once daily and rapid acting insulin analogs for at least one year
- From inclusion criterion I04: HbA1c <7% or >10%
- Major or critical deviation linked to exclusion criteria:
 - With E09: Patients having received basal insulin dose ≥ 0.6 U/kg body weight within 30 days prior to screening.
 - With E13: Patients who will need real time, flash or implantable CGM for routine care any time during study participation.
 - With E23: Inappropriate CGM use during run-in period evidenced by failure to obtain a minimum of 10 days (not necessarily consecutive) of useable CGM data by the end of run-in.
- Other major or critical deviation potentially impacting primary efficacy results:
 - Not taken only the treatment allocated by IRT (ie, wrong treatment taken at randomization or switch during the study)
 - Wrong stratum of randomization
 - Taken any prohibited medications for more than 10 consecutive days during the study as follows:
 - Any glucose-lowering agents other than IMP, the patient's current background basal insulin analog during the run-in period (which may not be changed during the study), or the patient's existing mealtime insulin (which may not be changed during the study). This includes oral or injectable glucose lowering agents, other type of basal insulin (eg, NPH), pre-mixed insulin, and human regular insulin
 - Insulin pump therapy.
 - Systemic glucocorticoids (topical or inhaled applications are allowed).
 - Patient who did not receive the CGM at Week 9, or for whom there are issues with uploading the CGM data at Week 12. This will be evaluated for patients who completed the treatment period and the study

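### The HbA1c ANCOVA alone omits the HbA1c stratum used to randomize; adding it is a free improvement with a small expected gain

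*SAP*

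**What the plan says.** Protocol 6.3 states: "Randomization will be stratified by HbA1c at screening", with the cut at 8.0%. This is the only stratification factor. Protocol 8.1.2 gives its source: "The screening value will be transferred into the IRT for stratification purpose during the patient randomization at the Visit 6". HbA1c is measured at screening (Week -6/-5) and again at "randomization Visit 6 and Visit 18 (Week 12").

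SAP 2.1.1 defines the covariate: "The baseline value is the last available value obtained up to the date and time of randomization". For HbA1c this is normally the Visit 6 sample.

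SAP 2.4.4.2.2 models change in HbA1c on treatment group "as well as the continuous fixed covariate of baseline HbA1c value". Protocol 9.4.1, Table 7, has the same: "model including fixed categorigal effect of treatment group (Toujeo, Tresiba), as well as, the continuous fixed covariate of baseline HbA1c value". The protocol synopsis and SAP Appendix A agree. The two documents do not contradict each other.

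The stratum is a model term for the primary endpoint (SAP 2.4.4.1.1), the CGM secondary endpoints (2.4.4.2.1), FPG (2.4.4.2.3), the within-day CV subgroup analysis (2.4.4.2.4) and the patient-reported outcomes (2.4.7). It is also in the SAP's hypoglycemia models (2.4.5.1). SAP 1.5 and 1.6 give no reason for treating HbA1c differently.

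**The concern.** The usual practice is to analyze by the factors used to randomize. If a stratum predicts the outcome beyond the covariates already in the model, leaving it out makes the reported standard error a little larger than it needs to be.

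Here the omission falls on the outcome that shares its analyte with the stratification factor. Continuous baseline HbA1c would make the stratum wholly redundant only if both came from the same sample and the relation were linear. They come from samples about five to six weeks apart, and the run-in lies between them, with titration of basal and mealtime insulin (protocol 4.1, 4.3). A patient can be on one side of 8.0% at screening and on the other at Visit 6.

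What is at stake is the precision of a named secondary endpoint, and a difference between models that a reader of the report will notice and find unexplained.

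**Working it through.** **The plan's own figure.** The documents state no SD, interval width or power for HbA1c, so there is nothing to reproduce for this endpoint. The plan supplies only the sample sizes: 2 × 131 = 262 evaluable and 338 randomized.

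**What the result depends on.** Let S be screening, B baseline (Visit 6) and W Week 12 HbA1c, and let Z be the stratum (S of 8.0% or more). With 1:1 stratified allocation, in large samples,

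SE with stratum / SE without = √[ Var(W−B given B, Z) / Var(W−B given B) ].

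The ratio is below 1 only if screening predicts Week 12 beyond baseline. If the S–W correlation equals the product of the S–B and B–W correlations, screening adds nothing and the ratio is 1.

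**Inputs.** From the documents: stratified 1:1 allocation with a cut at 8.0%, and screening HbA1c of 7% to 10% (the per-protocol deviation rule reads "From inclusion criterion I04: HbA1c <7% or >10"%). Assumed, because the documents are silent: mean 8.3, SD 0.8, block size 4 and all correlations.

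**Results.** Columns 3 to 5 are the mean 95% CI half-width (HbA1c percentage points) over 1,500 simulated trials at N = 338. The last column is the large-sample change in SE from the ratio above, computed on 4 million simulated patients before truncation.

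| Correlations S–B / B–W / S–W | Product S–B × B–W | Without stratum | With stratum | Change | Large-sample change |
|---|---|---|---|---|---|
| 0.90 / 0.75 / 0.675 | 0.675 | 0.1133 | 0.1134 | +0.06% | 0.0% |
| 0.90 / 0.75 / 0.70 | 0.675 | 0.1132 | 0.1132 | −0.02% | −0.1% |
| 0.90 / 0.70 / 0.60 | 0.63 | 0.1222 | 0.1221 | −0.03% | −0.1% |
| 0.80 / 0.70 / 0.56 | 0.56 | 0.1224 | 0.1225 | +0.05% | 0.0% |
| 0.80 / 0.70 / 0.60 | 0.56 | 0.1222 | 0.1221 | −0.10% | −0.2% |
| 0.80 / 0.70 / 0.65 | 0.56 | 0.1219 | 0.1210 | −0.74% | −0.8% |
| 0.70 / 0.60 / 0.42 | 0.42 | 0.1369 | 0.1369 | +0.03% | 0.0% |
| 0.70 / 0.60 / 0.50 | 0.42 | 0.1367 | 0.1363 | −0.35% | −0.4% |
| 0.70 / 0.60 / 0.60 | 0.42 | 0.1359 | 0.1331 | −1.99% | −2.0% |

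At N = 262 the percentage changes are nearly the same (+0.08% to −1.99%). The small positive values are the finite-sample cost of one more term.

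**The favorable end.** The last row sets S–W equal to B–W, so that screening predicts Week 12 as well as the later value. Other large-sample cases of that kind:

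- 0.90 / 0.75 / 0.75: −0.9%
- 0.80 / 0.70 / 0.70: −1.9%
- 0.90 / 0.90 / 0.90: −3.0%
- 0.70 / 0.70 / 0.70: −3.5%
- 0.80 / 0.80 / 0.80: −3.6%

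This is where the ceiling of about 4% comes from.

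**Validity.** Coverage of the 95% interval with baseline HbA1c alone was 0.937 to 0.963 over the 18 simulated settings. Simulation error is about ±1.96 × √(0.95 × 0.05 / 1500) = ±0.011 in each. In every setting coverage was within 0.005 of the model with the stratum, so the scatter is common to both models.

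**Size in HbA1c units.** In the last row of the table the half-width falls by 0.1359 − 0.1331 = 0.0028 percentage points.

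**What baseline already does.** Replacing continuous baseline by the stratum alone would widen the interval by 2.4% to 12.1%. The stratum should be added to baseline and should not replace it.

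**The case against.** The strongest reply is that the comparison with the other models is not like for like. The CGM, FPG and patient-reported outcome models adjust for their own baseline variable, so the stratum is their only HbA1c term. In the HbA1c model it would be a second, dichotomized HbA1c term next to a continuous and more recent one. The omission is the same in all four places where the model is stated, each time alongside an FPG model that has the stratum, so it may be deliberate. Treatment plus continuous baseline is a valid ANCOVA. Most of this stands, and it is why the gain is small. It does not make the stratum fully redundant, because the two samples differ, and the documents do not give this or any other reason.

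A reader might infer more than the documents support:

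- **That the interval ignores the stratified design or is invalid.** It does not: continuous HbA1c at randomization recovers most of the stratum's information, and coverage is unharmed.
- **That a loss of several percent in precision is to be expected.** That requires screening to predict Week 12 as well as baseline does. Nothing in the documents shows this, and the older sample and the intervening titration make it less likely.
- **That a conclusion of similar HbA1c is at risk.** The protocol only anticipates similarity (2.1, 3.1). There is no HbA1c margin, equivalence test or power claim.

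**Conclusion.** The point holds as a small improvement and not as an error in the plan. The HbA1c ANCOVA is the only between-arm efficacy model in the SAP that leaves out the randomization stratum, and no rationale is stated. The planned interval is valid and at most slightly conservative.

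Adding the stratum would lower the SE by about 0% to 2% under most assumed correlations, and by up to about 4% only under equal prediction by screening and baseline. These figures rest on an assumed mean, SD and correlations. They include zero, so no gain can be established from the documents alone. In large samples the stratum cannot raise the residual variance, and at this trial's size its cost was below 0.1% of the interval width.

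The HbA1c interval and p-value are descriptive (SAP 2.4.4.2.2) and outside the testing hierarchy (SAP 2.4.4.3), so no confirmatory conclusion changes.

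**What to change.** Add the randomization stratum of screening HbA1c, already defined as HBACRIT1 in SAP 2.5.3, as a fixed categorical effect in the HbA1c ANCOVA, as in the FPG model. Keep continuous baseline HbA1c. The terms become treatment group, stratum and baseline HbA1c.

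Make the change in SAP 2.4.4.2.2 and the HbA1c row of Appendix A, and align the protocol synopsis and Table 7. If only the SAP is changed, record the departure from the protocol in SAP 1.5.

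The cost is one model term and one degree of freedom, with no new data and no effect on sample size or the testing hierarchy. If the sponsor prefers the present model, one sentence explaining why the stratum is left out is the minimum.

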2.4.4.2.3 FPG

Change in FPG will be analyzed using an ANCOVA model including the fixed categorical effects of treatment group (Toujeo, Tresiba) and the randomization stratum of HbA1c at screening (<8.0%, $\geq8.0\%$) as well as the continuous fixed covariate of baseline FPG value. LSmeans treatment difference (with the corresponding SEs and 95% CI) will be provided and p-value (of the difference between the two treatments) will be provided for descriptive purpose.

2.4.4.2.4 Subgroups analyses of secondary efficacy endpoints

Subgroup analyses will be performed on glucose within-day CV to summarize the treatment effects across subgroup defined by glucose within day $CV \le 36\%$ vs. >36% at baseline. The ANCOVA model will be used, the randomization stratum of HbA1c at screening, CV subgroup at baseline, as well as the interaction of treatment group by CV subgroup at baseline are included as fixed effects. LS means treatment difference (with the corresponding SEs and 95% CI) will be presented for each subgroup. The p-value for the interaction fixed term will be obtained in order to evaluate whether the corresponding subgroup is behaving as a response modifier.

2.4.4.3 Multiplicity issues

To control the type I error, a hierarchical step-down testing procedure described by Hochberg and Tamhane (4) will be applied for the primary efficacy endpoint and the main secondary endpoint:

- Step 1 assesses non-inferiority of Toujeo versus Tresiba on the percent time in the range of 70-180 mg/dL,
- Step 2: only if Step 1 is demonstrated, then non-inferiority of Toujeo versus Tresiba on the glucose total CV will be tested with a relative non-inferiority margin of 10%,
- Step 3: only if Step 2 is demonstrated, then the difference between Toujeo and Tresiba on the percent time in the range of 70-180 mg/dL will be tested.

No multiplicity adjustment will be made on other secondary/other efficacy variables; 95% CI and p-values presented for these endpoints will be done for descriptive purpose only.

